## DESCRIPTION OF THE RESEARCH PROJECT

### Hypothesis to be tested:

Concisely list in order, in the space provided, the hypothesis to be tested and the Specific Aim of the proposed study. Provide the scientific basis of the hypothesis, critically examining the observations leading to the formulation of the hypothesis.

Iron deficiency anaemia (IDA) is the single largest nutritional deficiency globally, and is a major health problem in the developing countries. *Helicobacter pylori* (Hp) infections are also very common in the developing countries. This important gastrointestinal pathogen causes chronic gastritis, which ultimately progress to gastric atrophy and may thus impair absorption of iron. We, therefore, hypothesize that in Bangladeshi women in the reproductive age:

1. chronic *Helicobacter pylori* infection is a major cause of low gastric acid output (hypochlorhydria), which in turn
2. significantly contributes to the development of iron deficiency anaemia in this population.

### Specific Aims:

Describe the specific aims of the proposed study. State the specific parameters, biological functions/ rates/ processes that will be assessed by specific methods (TYPE WITHIN LIMITS).

The two specific aims of this study are:

1. to determine the prevalence of hypochlorhydria and iron deficiency anemia in *H. pylori*-infected women in the reproductive age, in a peri-urban slum of Dhaka city, and
2. to determine the if *H. pylori* infection is causally linked to iron deficiency anemia in this population.

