In some other studies, *HP*-infection has actually been found to be associated with increased gastric acid output (El-Omar et al. 1995a). Thus, the relationship between *Hp* infection and gastric acid secretion remains to be fully elucidated. This discrepancy may be related to the site of infection-antral colonization may increase gastric acid secretion as has been observed in *Hp*-infected individuals with duodenal ulcer (El-Omar et al. 1995b). In a hospital-based study, gastrin-releasing peptide (GRP)-stimulated acid secretion was increased in significantly higher proportion of *Hp*-infected non-ulcer patients, compared to *Hp*-negative healthy subjects (El-Omar et al. 1995).

It was reported later by the same group (El-Omar et al. 1997) that *Hp* was predominantly responsible for gastric hypochlorhydria in a sub-group of *Hp*-infected Scottish subjects. Eradication of *Hp* resulted in variable degrees of restoration of gastric secretory function, ranging from minimal

Principal Investigator (Last, first, middle): [name]

increase to full restoration of gastric secretion. However, despite improvement in inflammation, eradication of *H. pylori* infection did not result in significant change in gastric atrophy and intestinal metaplasia, although partial recovery was observed in some of the subjects (El-Omar et al. 1997). Restoration of gastric acid secretion was observed after successful treatment of dyspeptic patients with HP infection in a recent study (Gutierrez et al. 1997). Finally, there is a serious lack in data from developing countries with regards to gastric functional abnormalities, specifically gastric acid secretion in Hp-infected population.

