Hp infection is considered a factor for anemia and IDA- Hp infection, common in such condition, has been discussed in the etiology of anemia and IDA (Dufour et al. 1993, Rosenstock et al. 1996, Marignani et al. 1997, Yip et al. 1997). This gastrointestinal pathogen has a worldwide distribution, however, it is more prevalent in the developing countries. The frequency of Hp infection is high in India, where >80% become infected by 20 years of age (Graham et al. 1991); in Bangladesh, where its prevalence in adults and children has been reported to be as high as 85% ([name] et al. 1995). Once infected, Hp infection is believed to remain throughout the life causing chronic gastritis, which is a risk factor for development of gastric atrophy and gastric cancer (Kuipers et al. 1995). Gastric acid is considered to be one of the most important luminal factors necessary for optimal absorption non-haeme Fe (reviewed by Skikne et al. 1981). It is possible that Hp infections may reduce absorption of Fe by causing gastric atrophy and achlorhydria, or by causing transient hypochlorhydria during the active infections. Both of these mechanisms would result in an increased susceptibility to IDA. Furthermore, increased fecal blood loss in Hp-infected individuals may contribute to IDA (Yip et al. 1997).

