### **3. Importance of *H. pylori* infection in IDA and Food fortification program to combat Fe deficiency**

Fe fortification of food is believed to be the most cost-effective approach to reduce Fe deficiency (Hurrell 1997, 1998). While Fe fortification programs have been relatively successful in industrialized countries, they had limited success in the developing countries (Hurrell 1997). This perhaps reflects differences in the aetiology of IDA in the developed versus the developing countries. If IDA is related to a lower bioavailability of Fe from diets such as cereals and legumes, fortification of such diets may not be the ideal method for Fe supplementation, unless it is protected from the inhibitors of absorption such as phytate. Ascorbic acid (Davidsson et al. 1994a, 1997, 1998) or Na2EDTA (INACG 1993) could be suitable for this purpose. If IDA is partly due to increased blood loss from gastrointestinal parasites, then their treatment will be required for the food fortification program to be maximally effective. Similarly, treatment of malaria and Hp-infection could be important. Treatment of these infections in the developing countries would be very expensive and impractical due to higher incidences of treatment failure/reinfection. Thus, addressing these issues is critical for implementation of a successful Fe-fortification program in such countries.

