## 2. Part 2: Testing of the second objective

### Randomized, double-blind, placebo-controlled, community trial

#### 2.1 Methods

To determine if there is a causal relationship of IDA with Hp infection, or if Hp infection has any relationship with IDA, an intervention study will be conducted on 100 Hp-infected women with hypochlorhydria and IDA. They will be randomized in equal numbers to receive either of the following four interventions:

- (i) Anti Hp therapy: A combination of 500mg clarithromycin twice daily + 500mg amoxicillin twice daily + 40 mg omeprazole once daily for 14 days
- (ii) Anti Hp therapy plus iron: The above + ferrous fumarate containing 60-mg elemental iron each day for 60 days
- (iii) Iron alone: Ferrous fumarate containing 60-mg elemental iron each day for 60 days
- (iv) Placebo: Starch powder

**Fifth group:** There will be a fifth group of 25 women with Hp infection but without hypochlorhydria. This group is required to observe the influence of hypochlorhydria *per se* on IDA. This group will also be treated with Anti-Hp therapy plus iron.

The therapies will be provided in gelatin capsules and will be fed daily in morning and at the evening. The women in the placebo group will receive same amount of starch powder in identical capsules for 60 days. To keep the study blind, all therapies will be kept in identical container and will be fed by a health worker who will remain unaware of the nature of the study and the contents inside the bottles.

The women will be followed for six months after the end of intervention. Hb, SF, and sTfR will be determined at the end of intervention and also, 3 and 6 months after the intervention. Urea breath test will also be performed at the same time. EIT will be repeated 6 months after intervention. The women in the placebo groups will be given anti-Hp therapy plus iron as indicated above at the end of study period of 6 months. Similarly the group (iii) women will also provided anti-Hp therapy at the end of the study. The dose of iron conforms to that used in Bangladesh ( Kolsteren et al 1999).

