### 2.3 Sample size

The sample size is determined with the assumptions that anaemia will be corrected in 95% women with Anti-Hp therapy plus iron-therapy, while iron therapy alone will correct anaemia in 60% of the women. Thus, the worthwhile difference (D) in correction of anemia will be:

$$D = 95 - 60 = 35\%$$

At 5% level of significance (type I error of 5%) with 80% power (type II error of 20%), and to detect a 35% difference in the outcome (correction of anaemia), the sample size has been estimated as follows:

$$n = 2 P(1-P) * (Z_{\alpha/2} + Z_{\beta})^2 / D^2$$

Where:  $P = (P_1 + P_2) / 2 = (95 + 60) / 2 = 77.5 \%$   
(  $P_1$  is 95% and  $P_2$  is 60% )

$$\begin{aligned} n &= 2 * 0.775 (1-0.775) * (1.96 + 0.86)^2 / (0.35)^2 \\ &= 1.55 * 0.225 * (2.82)^2 / 0.1225 \\ &= 0.34875 * 7.95 / 0.1225 \\ &= 22.6 \\ &\cong 23 \text{ subjects in each of the five groups} \end{aligned}$$

Based on previous study in the same community, we anticipate a drop out rate of approximately 10%. Therefore, the number of women to be enrolled is 25 in each group i.e.  $25 * 5 = 125$  women in total in 5 groups.

The reported prevalence of Hp infection is 80%. We estimate 60 % of infected population will be hypochlorhydric. of whom 70% will have IDA. We need to screen 298 ( $100 / 0.8 * 0.6 * 0.7$ ) women to identify 100 infected women (for four groups) with hypochlorhydria and iron deficiency anemia. As 160 women will be enrolled under the first part of the study we will require 138 ( $298 - 160 = 138$ ) additional women to be screened under the second part of the study.

We need a fifth group of 25 women with Hp infection but without hypochlorhydria. They will be selected from among these 260 women.

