### 2.4 Exclusion Criteria

Women with the following conditions will not be eligible for this study:

- Acute infection, or apparent inflammatory process

Principal Investigator (Last, first, middle): [name]

- Severe anemia (Hb of < 8g/dL)
- Severe malnutrition (body mass index <14)
- Presence of occult blood in stool as detected by HemoQuant test ( Schwartz et al 1983).
- History of chronic blood loss e.g. polymenorrhoea
- Presence of *Ancylostoma duodenale* (hook worm) in stool
- Pregnant and lactating women ( initial 2 months of lactation )

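### Aim 2 of the H. pylori protocol asks a therapy trial to settle whether Hp causes IDA, so a null result could not separate no causal link from infection not cleared or damage not reversed

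*Protocol*

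**What the plan says.** Specific Aims gives the second aim as finding out whether "infection is causally linked to iron deficiency anemia in this population". The opening of Research Design and Methods repeats this as the purpose of the randomised part. Section 2.1 puts it more broadly: "To determine if there is a causal relationship of IDA with Hp infection, or if Hp infection has any relationship with IDA". Four arms are randomised: anti-Hp therapy, anti-Hp therapy plus iron, iron alone and placebo.

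The hypothesis section describes a chain from chronic Hp infection through gastritis and atrophy to low acid output, and from there to IDA. On whether that chain reverses, Background section 1 cites a study in which eradication "resulted in variable degrees of restoration of gastric secretory function, ranging from minimal" up to full, and in which treatment "did not result in significant change in gastric atrophy and intestinal metaplasia, although partial recovery was observed in some of the subjects". It also cites a second study that did see acid secretion restored. Background section 3 says of treating infections in developing countries that it "would be very expensive and impractical due to higher incidences of treatment failure/reinfection".

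Section 2.3 assumes that "anaemia will be corrected in 95% women with Anti-Hp therapy plus iron-therapy", against 60% on iron alone, and arrives at 23 women per group (25 enrolled). It gives no source for either rate and no assumed rate of clearance or acid recovery.

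Section 2.1 repeats the breath test at the end of treatment and at 3 and 6 months, and EIT at 6 months. Section 2.6.1 lists Hp infection, hypochlorhydria and acid output as outcomes. For change in acid output, Data Analysis names a paired t-test within each group. It names no direct comparison of the arms on acid output, and nothing that ties the anaemia result to the clearance or acid recovery achieved.

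**The concern.** A randomised comparison of therapy answers a question about therapy. It also answers whether infection caused the anaemia only if therapy removes both the infection and its lasting effect on acid. The protocol's background gives grounds to doubt the second condition. Hp could have produced IDA through atrophy that treatment does not undo, and the treated and untreated arms would then look alike although the hypothesis is true.

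At stake is the reading of a null. Aim 2 is worded as a yes-or-no question about causation, and the plan gives no guidance for telling apart three explanations: no causal link, infection not cleared, or damage not reversed.

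**Working it through.** **1. The plan's own figure.** Inputs from section 2.3: P1 = 0.95, P2 = 0.60, mean P = 0.775, D = 0.35, z values 1.96 and 0.86.

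n = 2 × 0.775 × 0.225 × (2.82)² / 0.35² = 0.34875 × 7.9524 / 0.1225 = 22.64, so 23 per group. This reproduces.

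Power at 23 per arm for 95% v 60% is 81% by the protocol's formula, 83% by the Fleiss formula, and 88% by exact enumeration of the Pearson chi-square test. The stated 80% is sound under its own assumptions.

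**2. What 95% implies.** Let f be the share of the anti-Hp plus iron arm that is both cleared of Hp and acid-restored, and let r be the correction rate in those women. Suppose all other women in the arm respond as on iron alone (60%), and that restoration is independent of who would respond to iron. These are assumptions; the documents give neither f nor r.

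P1 = 0.60 + f × (r − 0.60)

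- r = 1.00: f = 0.35 / 0.40 = 0.875
- r = 0.98: f = 0.35 / 0.38 = 0.921
- r = 0.95: f = 0.35 / 0.35 = 1.00

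**3. What 80% power needs (r = 1.00).** With 23 per arm the exact test reaches 80% power at P1 = 0.928, so f = 0.328 / 0.40 = 0.82. With 25 per arm it does so at P1 = 0.917, so f = 0.79. The Fleiss formula gives 0.85 and 0.82, and the protocol's formula 0.865 and 0.84.

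**4. How power falls (exact chi-square, two-sided 5%).**

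| f | P1 (r = 1) | 23 per arm | 25 per arm |
|---|---|---|---|
| 0.875 | 0.95 | 88% | 91% |
| 0.80 | 0.92 | 77% | 81% |
| 0.70 | 0.88 | 61% | 65% |
| 0.60 | 0.84 | 45% | 49% |
| 0.50 | 0.80 | 32% | 35% |

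Power passes 50% at about f = 0.63 with 23 per arm. If restored women are corrected at 95% instead of 100%, power at 23 per arm is 61% at f = 0.80, 47% at 0.70 and 25% at 0.50.

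**5. The aim against the population.** Background 2.b names a second route, in that "increased fecal blood loss in Hp-infected individuals may contribute to IDA", while section 2.4 excludes women with "Presence of occult blood in stool as detected by HemoQuant test". The trial therefore mainly tests the acid route in hypochlorhydric women, which is narrower than a causal link of any kind.

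**The case against.** **The background is mixed.** The variable restoration came from a sub-group in one foreign population, and a second cited study saw restoration. This stands: the background makes incomplete reversal plausible, not established. The remark on treatment failure and reinfection concerns the practicality of treating several infections in developing countries. It should not be read as a forecast for capsules given by a health worker in this trial.

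**The mixture model is crude.** It counts partial restoration as none and assumes independence from iron response. Without independence, the strict requirement for 95% is that 35% of treated women are gained, which is 87.5% of the 40% who would fail on iron alone. This stands too, so the figures are illustrations.

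**Much of the remedy is already collected.** Breath test, hypochlorhydria and acid output are repeated outcomes, and Data Analysis allows a between-group chi-square test for binary variables, which could cover clearance. What is still missing is a direct comparison of the arms on acid output and a statement of how the anaemia result depends on it.

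**Other evidence bears on causation.** The anti-Hp-alone and placebo arms, and haemoglobin, ferritin and transferrin receptor as continuous outcomes, also contribute. They do, but each depends equally on clearance and reversal.

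**Stronger readings a reader might infer.** One is that 80% power requires at least 87.5% restored; that share is what the planned 95% needs, and 80% power needs somewhat less. Another is that a null is the likeliest result under partial reversal; under this model that is so only below about f = 0.63, and the documents give no f. A third is that the investigators would report a null as no causal link; no section sets a rule for a null.

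**Conclusion.** The point holds as one about the wording of the aim and the interpretation of the result. It is not an error in the sample-size arithmetic. Aim 2 claims more than a therapy contrast can deliver, given what the protocol itself says about reversibility. A null on anaemia would mean no demonstrated benefit of therapy. It would bear on causation only if clearance and acid recovery had been achieved.

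The planned effect rests on an unstated, high rate of clearance with recovery: 87.5% for the planned 95%, and roughly 79% to 87% for 80% power depending on method and on 23 or 25 evaluable women per arm. These shares are conditional on the mixture assumptions above.

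**What to change.** 1. In Specific Aims, the opening of Research Design and Methods, and section 2.1, restate Aim 2 as the effect of anti-Hp therapy on recovery from IDA in Hp-infected hypochlorhydric women.
2. In Data Analysis, compare the randomised arms directly on breath-test clearance and on EIT area under the curve, at least for anti-Hp plus iron against iron alone, instead of relying on within-group paired tests for acid output. Section 2.1 schedules both measurements at six months. State that a null on anaemia counts against a causal link only if the arms separate on both measures, and is otherwise reported as no demonstrated benefit of therapy.
3. Optionally, note in section 2.3 that the 80% power is conditional on high clearance and recovery, with power at lower shares shown.

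I would not add a complier-type ratio (anaemia difference divided by clearance difference). It does not address failed acid restoration, and the omeprazole in the regimen makes doubtful the assumption that therapy acts only through clearing Hp.

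The cost is a few sentences and two between-arm comparisons of data already being collected, plus a more modest claim for the trial. Enrolment and treatment are unchanged.

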## Background of the Project including Preliminary Observations

---

Describe the relevant background of the proposed study. Discuss the previous related works on the subject by citing specific references. Describe logically how the present hypothesis is supported by the relevant background observations including any preliminary results that may be available. Critically analyze available knowledge in the field of the proposed study and discuss the questions and gaps in the knowledge that need to be fulfilled to achieve the proposed goals. Provide scientific validity of the hypothesis on the basis of background information. If there is no sufficient information on the subject, indicate the need to develop new knowledge. Also include the **significance and rationale** of the proposed work by specifically discussing how these accomplishments will bring benefit to human health in relation to biomedical, social, and environmental perspectives. (DO NOT EXCEED 5 PAGES, USE CONTINUATION SHEETS).

---

### 1. *H. pylori* infections and gastric acid secretion

*Hp* is a major gastrointestinal pathogen, which occurs naturally and inhabits the protective, mucus layer of the gastric epithelial cells. It is the most frequent, known cause of chronic gastritis, and it also plays an important role in the etiology of peptic ulcer disease, gastric cancer, and non-ulcer dyspepsia.(reviewed by McGowan et al. 1996). The bacterium is highly adaptive to the unusual ecological niche in the human stomach, perhaps due to its production of large amounts of urease, an enzyme that hydrolyzes urea to ammonia and carbon dioxide leading to its better survival. An important adaptation of *Hp* to the gastric environment may be related to its ability to alter gastric physiology and function. Although the present discussion is related to Fe nutrition, reduced gastric acid output has other adverse consequences. For example, low gastric acid secretion is associated with increased susceptibility to enteric infections, a major public health problem, and has also been linked to diarrhea, malnutrition and growth failure in children in the developing countries (Weaver 1995).

Acute *Hp* infection causes gastritis and transient hypochlorhydria, however its mechanism is unclear. One hypothesis is that the parietal cell functions are directly affected by this pathogen (McGowan et al. 1996). Another possible explanation is the increased production of interleukin-1, a cytokine with powerful inhibitory action on acid secretion (Wallace et al. 1991). The most severe outcome of chronic, *Hp*-induced gastritis is gastric atrophy, which leads to decrease gastric acid secretion and eventually results in achlorhydria. Individuals with reduced gastric acid output may absorb some Fe fortification compounds less well, while those with achlorhydria will have reduced absorption of all non-heme Fe (Skikne et al. 1981).

In some other studies, *HP*-infection has actually been found to be associated with increased gastric acid output (El-Omar et al. 1995a). Thus, the relationship between *Hp* infection and gastric acid secretion remains to be fully elucidated. This discrepancy may be related to the site of infection-antral colonization may increase gastric acid secretion as has been observed in *Hp*-infected individuals with duodenal ulcer (El-Omar et al. 1995b). In a hospital-based study, gastrin-releasing peptide (GRP)-stimulated acid secretion was increased in significantly higher proportion of *Hp*-infected non-ulcer patients, compared to *Hp*-negative healthy subjects (El-Omar et al. 1995).

It was reported later by the same group (El-Omar et al. 1997) that *Hp* was predominantly responsible for gastric hypochlorhydria in a sub-group of *Hp*-infected Scottish subjects. Eradication of *Hp* resulted in variable degrees of restoration of gastric secretory function, ranging from minimal

Principal Investigator (Last, first, middle): [name]

increase to full restoration of gastric secretion. However, despite improvement in inflammation, eradication of *H. pylori* infection did not result in significant change in gastric atrophy and intestinal metaplasia, although partial recovery was observed in some of the subjects (El-Omar et al. 1997). Restoration of gastric acid secretion was observed after successful treatment of dyspeptic patients with HP infection in a recent study (Gutierrez et al. 1997). Finally, there is a serious lack in data from developing countries with regards to gastric functional abnormalities, specifically gastric acid secretion in Hp-infected population.

## 2. Iron deficiency anemia

Iron (Fe) deficiency anemia (IDA) is a major nutritional problem in the world that affect millions of people in the developing countries, particularly infants, children and women of child-bearing age (Bothwell et al. 1979, DeMaeyer & Adiels - Tegman 1985). The consequences of IDA include higher perinatal morbidity and mortality among mothers and children; impaired immune function and increased susceptibility to infections; decreased work performance; poor growth and potentially irreversible effects on cognition and motor function during early life (Scrimshaw 1984, Dallman 1987, Lozoff et al. 1991, Walter 1992). Thus, prevention and treatment of IDA are important in delivering health care to such population.

